## 12.2.2 Secondary Efficacy Analyses

### Secondary endpoints

#### **Safety endpoint**

All adverse events recorded during the study will be summarized by each subject cohort. The incidence of treatment-emergent adverse events (new or worsening from baseline) will be summarized by severity and type of adverse event. Listings of deaths, SAEs, and AEs leading to early termination of study treatment or premature withdrawal from study will also be provided.

#### **Duration of response (DOR)**

Duration of response is defined as the interval from the date of complete or partial remission documented to date of recurrence/progression, death due to any cause, or lost to follow-up. The Kaplan-Meier method will be used to estimate the median duration of response and its 95% confidence interval (CI).

#### **Progression-free survival (PFS)**

PFS is defined as the time from the date of start of treatment to the date of event defined as the first documented progression or death due to any cause. If a subject has not had an event, progression-free survival is censored at the date of last adequate assessment or start of another therapy, whichever occurs first. The Kaplan-Meier method will be used to estimate PFS and its 95% CI.

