## 1.0 PROTOCOL SYNOPSIS

Title	A Phase 2 study of Oral Ruxolitinib Phosphate for the Treatment of Relapsed or Refractory Diffuse Large B-cell and Peripheral T-cell Non-Hodgkin Lymphoma
Protocol IND Number	112445
Study Phase	II
Study Design	This is an open-label, multicenter, Phase II study
Planned Number of Study Sites and Planned Number of Subjects	Four study sites will participate. Approximately 90 subjects will be enrolled
Coordinating Investigator	[name].
Study Objectives	
Primary Objective: Assess the overall response rate (ORR) of subjects with diffuse large B-cell BCL and peripheral T-cell non-Hodgkin lymphoma (PTCL) who are relapsed or refractory to front-line treatment and ineligible for stem cell transplantation or have recurrent disease after stem cell transplantation to oral ruxolitinib.
 
Secondary Objectives: Evaluate safety of oral ruxolitinib therapy in subjects with DLBCL and PTCL  Determine progression free survival (PFS), duration of response, and overall survival (OS) in subjects with DLBCL and PTCL
 
Exploratory Objectives: Explore relationship between responses to oral ruxolitinib and alterations in GEP signatures as well as biomarker immunophenotypic changes related to JAK2/STAT3, NF-κB, BCR, PI3K/AKT, and mTOR pathways.  Evaluate potential effect of oral ruxolitinib exposure on JAK2/STAT3 pathway inhibition in serial tumor samples.

Dose and Mode of Administration and Duration of Treatment	Subjects will receive continuous dosing with oral ruxolitinib for 28 day cycles. The study is comprised of 3 phases:  Screening: up to 28 days On-Treatment Phase: participation may continue for subjects receiving benefit and who have not met any reason for study discontinuation Follow-up: Subjects will be followed after discontinuation from the study to assess disease status, subsequent therapies and survival. Follow-up will occur by a clinic visit or telephone contact every 3 months for the 1 st year and every 6 months thereafter.

	
Evaluable subjects will include subjects who have received at least 2 cycles of therapy, or subjects with documented progression of disease prior to completion of 2 cycles of therapy.

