#### **7.4 Duration of Participation**

Subjects who are demonstrating benefit may continue to receive treatment with ruxolitinib unless a criterion for discontinuation from the study has been met. The criteria for study discontinuation are listed below:

- unacceptable toxicity;
- disease progression or relapse
- investigator discretion
- withdrawal of consent
- pregnancy

If a subject is withdrawn from the study treatment for any reason, the study sponsor-investigator must be notified and an end-of-treatment visit should be performed. Follow-up evaluations will also be performed in accordance with the protocol requirements.

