## **7.6 Follow-up Evaluations**

Subjects will be followed every 3 months for the first year and every 6 months thereafter via a clinic visit or contact by telephone by research staff personnel to obtain the following information:

- Disease Status will be collected until first documented relapse or progression of the disease under study;
- Date last alive or date of death

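### As worded, the PFS rule counts events after another therapy but censors at the switch those with no event by the data cut-off, so the Kaplan-Meier estimate depends on follow-up length

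*Combined protocol and SAP*

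**What the plan says.** The PFS paragraph of section 12.2.2 runs the endpoint from start of treatment to "the date of event defined as the first documented progression or death due to any cause". It sets no limit to events before a new therapy. Censoring comes next: "If a subject has not had an event, progression-free survival is censored at the date of last adequate assessment or start of another therapy", whichever is earlier. The estimator is stated as "The Kaplan-Meier method will be used to estimate PFS and its 95% CI". Section 12.2 places secondary efficacy analyses in the ITT population.

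Off-treatment data collection is in section 7.6. Contact is scheduled as "Subjects will be followed every 3 months for the first year and every 6 months thereafter", with no stated end. Two items are collected: "Disease Status will be collected until first documented relapse or progression of the disease under study" and "Date last alive or date of death". Neither stops when another therapy starts. The synopsis adds that "Subjects will be followed after discontinuation from the study to assess disease status, subsequent therapies and survival".

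Section 7.4 lists reasons for stopping other than progression, including "unacceptable toxicity", investigator discretion and withdrawal of consent. A switch before progression is therefore possible. No section gives a PFS data cut-off date, a PFS sensitivity analysis, or another rule for events that follow a new therapy.

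**The concern.** Kaplan-Meier requires that, at any time, a censored subject is no more and no less likely to fail later than those still at risk. Here, whether a switcher is censored at the switch is settled by what happens afterwards. Those who fail before the cut-off keep all their time after the switch and count as events. Those who have not yet failed lose that time and leave the risk set early. The censoring date depends on the later outcome and on when the data are cut.

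The resulting number has no clear interpretation. It is not PFS with new therapy treated as a censoring event, nor PFS regardless of new therapy. Two data cuts of the same trial could give different 6-month PFS values for this reason alone. PFS is a named secondary objective, and a reader would compare the reported value with other single-arm results that use one of the two usual rules.

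**Working it through.** **The rule on single subjects.** A subject switches at month 3 and dies at month 9. With the data cut at month 8 there is no event, so the subject is censored at 3. With the cut at month 10 the subject is an event at 9. Next, take two subjects who both switch at month 2. One progresses at month 10 and is an event at 10. The other is still progression-free at the cut and is censored at 2.

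**Inputs.** The event definition, censoring rule and estimator are from section 12.2.2. The target of 30 per cohort (cohorts 1 to 3) is from section 12.2.1. The plan states no PFS figure, so there is none to reproduce. Everything else is assumed: exponential event times, an exponential switching time independent of prognosis, the share switching before progression, the hazard after the switch, and uniformly distributed follow-up.

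**Set-up.** With a median of 3 months the monthly hazard is λ = ln 2 / 3 = 0.231, so true 6-month PFS is exp(−0.231 × 6) = 25%. For a share s switching before an event, the switching rate is μ = λs/(1 − s):
- s = 10%: 0.231 × 0.1/0.9 = 0.026 per month
- s = 30%: 0.231 × 0.3/0.7 = 0.099 per month

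Three Kaplan-Meier estimates were compared on large simulated samples (at least 100,000 subjects per scenario): the rule as written; everyone censored at the switch; and the switch ignored with all events counted.

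**6-month PFS under the rule as written, assumed median 3 months**

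| Switch before progression | Hazard after switch | Follow-up 3–9 mo | 6–18 mo | 12–24 mo | Consistent rules |
|---|---|---|---|---|---|
| 10% | unchanged | 23.4% | 24.4% | 24.9% | 25% under both |
| 30% | unchanged | 19.4% | 23.0% | 24.5% | 25% under both |
| 30% | halved | 21.5% | 25.8% | 28.3% | about 25% (censor everyone); 30.5% (count all) |

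With no switching before progression, the three estimates are identical. In the 30%, unchanged-hazard, 3–9 month case the median is 2.83 against 2.99 months.

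**A longer median.** Assume a 6-month median, 20% switching, 12 months of uniform accrual, and minimum follow-up of about 0, 6, 12, 24 and 60 months. Then 12-month PFS as written is:
- hazard unchanged: 20.2%, 21.6%, 23.0%, 24.6%, 24.9%, against about 25% under both consistent rules
- hazard halved: 22.2%, 23.0%, 24.4%, 26.5%, 28.2%, against about 25% (censor everyone) and 28.5% (count all)

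The largest gap found was with a 6-month median, 30% switching, unchanged hazard and the shortest follow-up: 12-month PFS 16.5% against 24.7%, a gap of 8.2 points. Follow-up there ends at 12 months, so that value sits at the very end of the curve.

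**Scale.** The standard error of a proportion near 25% with 30 subjects and no censoring is √(0.25 × 0.75/30) = 0.079, or 7.9 points. The 19.4% case differs from 25% by 5.6 points, and 5.6/7.9 = 0.71 of a standard error. The 8.2-point case is just over one standard error.

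**The case against.** The strongest reply is that the sentence can be read sequentially: a subject who is event-free when another therapy starts is censored at that moment, and later events are ignored. Under that reading there is no outcome-dependent censoring, and the author may well have meant it. But the text does not say so. The condition is the absence of an event, with no time attached, and the event definition has no exclusion. Two programmers could follow the sentence and produce different curves.

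Other replies largely stand. Subjects who benefit may stay on treatment, and concurrent anti-cancer therapy is prohibited (section 9.4.2), so a switch before progression first requires stopping for another reason and may be uncommon. Follow-up has no stated end, and with an unchanged hazard the distortion fades as it lengthens. Capture of progression after a switch is inferred: the follow-up column of the section 7.1 flowchart shows only subject status, with no imaging, and contact may be by telephone. Deaths would be captured in any case. In most scenarios the effect is smaller than sampling error, although the planned confidence interval reflects sampling error and not this distortion.

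A reader might infer that reported PFS will certainly be too low, by some 5 to 6 points. The documents do not support that. They give no median, switching rate or data cut. The direction against the censor-everyone rule can reverse when later therapy lowers the hazard, and the size can be nil.

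**Conclusion.** The point holds for the wording of section 12.2.2. Read literally, time after a switch counts only for subjects with an event by the data cut-off, and the PFS estimate then drifts with follow-up. The relevant group is subjects with no event by the cut-off, not subjects who never have one; that is why the estimate moves as data mature.

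The size is unknown. With a 3-month median and an unchanged hazard, 6-month PFS is 19.4% to 24.9% against 25% across 10% to 30% switching and follow-up from 3–9 to 12–24 months. With a halved hazard and 30% switching it goes from 21.5% to 28.3%, starting below both consistent rules and ending between them. All of this rests on assumed switching rates, exponential times and switching unrelated to prognosis.

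A reader might also infer that the go/no-go conclusion is at risk. It is not: that decision uses ORR alone (section 12.2.1), and PFS has no test, threshold or comparator. This is a correction worth making before the data are analysed, not a threat to the design.

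**What to change.** In the PFS paragraph of section 12.2.2, apply one rule to all subjects. For example: every subject who starts another anti-lymphoma therapy before documented progression is censored at the last adequate assessment on or before that start, whether or not an event follows. Report as a sensitivity analysis PFS that counts all progressions and deaths regardless of new therapy. The reverse choice of primary and sensitivity analysis is equally acceptable.

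State that censoring at the switch assumes switching is unrelated to prognosis. Subjects leaving for toxicity or at investigator discretion may not satisfy this, which is a reason to show both estimates. Fix the data cut-off for PFS. Say whether the same rule applies to duration of response, whose definition does not mention another therapy. Because the item list in section 7.6 omits subsequent therapy although the synopsis includes it, confirm that the start date of any new therapy is recorded.

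The cost is about one sentence for the main change and one extra Kaplan-Meier run. The synopsis already foresees follow-up of subsequent therapies.

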### **Overall survival (OS)**

OS is defined as the time from date of start of treatment to date of death due to any cause. If a subject is not known to have died, survival will be censored at the date of last contact. The Kaplan-Meier method will be used to estimate the median OS time and its 95% CI.

#### **12.2.3 Exploratory Analyses**

##### *Exploratory endpoints*

The exploratory aspect of the study is to explore relationship between responses to oral ruxolitinib and alterations in GEP signatures as well as biomarker immunophenotypic changes related to JAK2/STAT3, NF- $\kappa$ B, BCR, PI3K/AKT, and mTOR pathways, and to evaluate potential effect of oral ruxolitinib exposure on JAK2/STAT3 pathway inhibition in serial tumor samples. Descriptive statistics will be used. Mean, standard deviation (STD), median and range will be reported for markers pre- and post-treatment as well as for the marker changes between pre- and post-treatment. Paired t-test will be used to evaluate the marker changes between pre- and post-treatment. Spearman or Pearson correlation coefficients will be calculated to evaluate the correlations among markers. Logistic regression will be utilized to assess the effects of markers at baseline on response to therapy.

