### **12.2.1       Primary Efficacy Analyses**

Primary endpoint

The primary objective of the study is to evaluate subject overall response rate (ORR) after 6 cycles for each of the subject cohorts. The description provided in this section includes the primary analyses for the primary objective.

Statistical hypothesis and sample size justification

Subjects meeting the stated eligibility requirements will be enrolled onto the study. Subjects will be grouped into cohorts 1) DLBCL ABC 2) DLBCL GCB 3) PTCL and 4) OTHER SUBTYPES (subjects who are not able to be placed into cohorts 1, 2, and 3), based upon a central determination of immunohistochemistry and gene-expression profile. A target sample size of 30 is planned for cohorts 1, 2, and 3. Cohorts 1, 2, and 3 will have a minimum of 10 and a maximum of 30 subjects. There is no minimum or maximum requirement for Cohort 4, since there is a very low number of subjects anticipated for this cohort. (Maximum in all cohorts is 90 subjects).

These sample sizes are based on a 3-stage design of alpha=0.07 with power of 77% ( $\beta=0.23$ ) to test the null hypothesis that ORR after 6 cycles will be  $\leq 10\%$  (not considered clinically compelling) versus the alternative hypothesis that ORR will be  $\geq 25\%$  (considered clinically meaningful in this patient population) within each cohort. Based on the simulation study, to maintain the above type I and II errors, two interim analyses for futility will be performed for each cohort separately according to the following stopping rule:

- 1) The first interim analysis will occur when 10 subjects have been enrolled in the cohort. If there are any responders (CR+PR) observed among the 10 subjects, enrollment will continue; otherwise, enrollment will be suspended and these 10 subjects will be followed to further assess their responses. During this follow-up period, as soon as one response is observed, enrollment will resume. If no response is observed after the 10 subjects have been fully assessed after 6 cycles, the trial will be terminated for futility.

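### The marker–response logistic regression names no small-sample method, although a full cohort is expected to yield only about 3 to 8 responders

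*Combined protocol and SAP*

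**What the plan says.** Section 12.2.3 is exploratory and mostly descriptive. For the link between baseline markers and response, its only method is this sentence: "Logistic regression will be utilized to assess the effects of markers at baseline on response to therapy". It names no penalised or exact method, no limit on markers per model, no choice between pooled and per-cohort fitting, and no fallback if the fit fails. For change over time it says "Paired t-test will be used to evaluate the marker changes between pre- and post-treatment".

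The numbers available come from Section 12.2.1: "Cohorts 1, 2, and 3 will have a minimum of 10 and a maximum of 30 subjects", and "Maximum in all cohorts is 90 subjects". In each of these cohorts the design tests a response rate of 10% or less against 25% or more, with futility looks at 10 and 20 subjects. Under Section 5.2.1 a baseline tumour sample is mandatory for all subjects, so the regression could use nearly everyone. The listed markers include a mutation status (CARD 11) as well as staining and expression measures.

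**The concern.** The information in a logistic regression is limited by the smaller outcome group, here the responders. With few of them, maximum-likelihood log odds ratios are biased away from zero. Under separation, when a marker divides responders from non-responders perfectly, the estimate is infinite.

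Relating response to pathway and expression markers is a stated exploratory objective (Section 4.3). If a continuous marker's odds ratio is inflated, a later study planned around it would expect too large an effect. If the fit diverges, there is no usable estimate and the plan gives no alternative.

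**Working it through.** **1. The design's own figures.** Inputs from Section 12.2.1: stop if 0 of 10 respond; stop if fewer than 3 of 20; reject the null if at least 6 of 30. With a, b and c responders in successive tens:

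P(reject) = Σ P(a)·P(b)·P(c ≥ 6 − a − b), summed over a ≥ 1 and a + b ≥ 3.

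This gives 0.0663 at 10% and 0.7636 at 25%, against the stated alpha of 0.07 and power of 77%. The design reproduces to within rounding and about one point.

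**2. Responders available.**
- Full cohort: 30 × 0.10 = 3.0 (5th–95th percentile 1–6); 30 × 0.25 = 7.5 (4–12). Fewer than 10 responders occur with probability 99.95% and 80%.
- Pooled: 90 × 0.10 = 9 (5–14); 90 × 0.25 = 22.5 (16–29).
- Early stopping at 10%: 0.9^10 = 34.9% of cohorts stop at 10 with no responder, so no within-cohort model can be fitted. Another 35.3% stop at 20 with one or two. Expected cohort size is 19.5, or 58.5 over three cohorts, so pooling 90 is the favourable case.

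**3. Bias, one continuous marker.** The documents give no marker effect, so odds ratios of 2 and 3 per SD are assumed (log odds ratios 0.693 and 1.099), with a standard-normal marker, fixed sample size and 1,500 simulated trials per row. Bias = estimate ÷ true log odds ratio − 1. ML figures are over converged fits.

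| n | ORR | True OR | ML mean | ML median | Firth mean | RMSE, ML / Firth |
|---|---|---|---|---|---|---|
| 30 | 10% | 2 | 0.870 (+26%) | 0.730 (+5%) | 0.683 (−1%) | 1.23 / 0.82 |
| 30 | 25% | 2 | 0.838 (+21%) | 0.772 (+11%) | 0.712 (+3%) | 0.66 / 0.53 |
| 30 | 10% | 3 | 1.419 (+29%) | 1.210 (+10%) | 1.074 (−2%) | 1.42 / 0.87 |
| 30 | 25% | 3 | 1.320 (+20%) | 1.175 (+7%) | 1.117 (+2%) | 0.88 / 0.80 |
| 90 | 10% | 2 | 0.746 (+8%) | 0.714 (+3%) | 0.691 (0%) | 0.46 / 0.41 |
| 90 | 25% | 2 | 0.735 (+6%) | 0.722 (+4%) | 0.699 (+1%) | 0.30 / 0.28 |
| 90 | 10% | 3 | 1.210 (+10%) | 1.140 (+4%) | 1.109 (+1%) | 0.57 / 0.49 |
| 90 | 25% | 3 | 1.160 (+6%) | 1.138 (+4%) | 1.098 (0%) | 0.36 / 0.33 |

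On the odds-ratio scale, the fourth row is exp(1.320) = 3.7 for ML and exp(1.117) = 3.1 for Firth, against a true 3. A separate simulation at a true odds ratio of 2.5 gave ML bias of +24% to +30% at n = 30 and +6% to +13% at n = 90, with Firth at about −2% to +3%. Monte Carlo error is roughly 3 to 6 points for the n = 30 biases.

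Smaller cohorts at 25%, true odds ratio 2: ML +39% at n = 20 and +49% at n = 10, where 12% of fits fail. Firth is +5% at both.

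**4. Four markers in one model, true odds ratio 2.** At n = 30, ML is +52% to +55% with 24% (ORR 10%) and 1.5% (ORR 25%) of fits diverging; Firth is −9% to +5%. At n = 90, ML is +10% to +16%; Firth is −1% to 0%.

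**5. One binary marker, split 50:50 (assumed), true odds ratio 3, n = 30.** ML diverges in 48% of fits at ORR 10% and 9% at ORR 25%. The fits that converge are not overstated (−46% and −2%). Firth always gives a finite estimate here (−13% and −1%), with no gain in RMSE over the converged ML fits.

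**6. Testing.** With no marker effect and n = 30, the ML Wald test at two-sided 0.05 rejects in only 1.2% to 2.4% of trials. At a true odds ratio of 3 and ORR 25%, power is 50% for Wald and 58% for the penalised likelihood-ratio test.

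**The case against.** The text does not specify maximum likelihood, per-cohort fitting or multi-marker models. Where the protocol wants results by cohort it says so, for response in Section 12.2.1 and for adverse events in Section 12.2.2. A pooled fit is therefore at least as natural a reading, and pooled bias for one marker is modest. Means are also pulled up by extreme fits, and the medians shift much less. The n = 30 rows at 10% ignore the stopping rules, under which about 70% of such cohorts (34.9% + 35.3%) end earlier. The section is exploratory.

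Most of this stands and sets the size of the point. It does not remove it. An unqualified logistic regression is ordinarily a maximum-likelihood fit, the pooled bias is small but not zero, and early stopping leaves even fewer responders. Pooling also needs its own rule. Section 12.2.1 assigns cohorts from immunohistochemistry and gene expression, so a pooled model without a cohort term could confuse a marker with the subtype it helps define.

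A reader might go further and infer that every marker reported will be overstated. The binary-marker results contradict that. Nor does the fit create excess false positives, since the Wald test is conservative.

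A reader might also want the paired t-test replaced by a signed-rank test, Spearman made the only correlation, and gene-level false-discovery control added. The documents do not support treating these as defects. With five pairs the smallest two-sided signed-rank p-value is 2/2^5 = 0.0625, so 0.05 could never be reached. Spearman is already permitted. The section speaks of expression signatures and gives no number of gene-level tests from which false positives could be counted.

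**Conclusion.** The point holds as a minor, inexpensive improvement. The design supplies about 3 to 8 responders in a full cohort and at most about 9 to 23 over 90 subjects. In that range, standard logistic regression overstates a continuous marker's log odds ratio on average. For one marker the bias is about +20% to +30% in a cohort of 30 (median about +5% to +11%) and about +6% to +13% pooled; it is larger with several markers in one model. For binary markers or very few responders, the main risk is no finite estimate.

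These sizes rest on assumed true odds ratios of 2 to 3 per SD, normally distributed or 50:50 markers, and fixed sample sizes. The tabulated pooled runs are single-marker models and do not measure the effect of adding a cohort term. The harm is to effect size and estimability. The primary response decision is unaffected.

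**What to change.** In Section 12.2.3, replace the logistic regression with Firth-penalised logistic regression and profile-penalised-likelihood confidence intervals. Enter one marker per model, pooled over cohorts with a cohort term. State that per-cohort marker results will be reported descriptively when responders are very few, and give the responder count beside every estimate.

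The cost is a small change in SAP wording; no extra subjects or samples are needed. There are two downsides. Estimates shrink slightly when responders are very few (for example −13% for a binary marker at ORR 10% and n = 30). Pooling also assumes a similar marker effect across cohorts, which the descriptive per-cohort results let a reader judge.
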